6.13.1. Premature Drug Discontinuation

Subjects who prematurely discontinue study drug will be questioned regarding reasons for discontinuation. Subjects will be encouraged to restart study drug following the guidelines in section 6.12.2.

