6.13.2. Restarting Study Drug after Premature Drug Discontinuation

Subjects who discontinue study drug for less than one week will be asked to restart at the prior dose. Those who failed to take study drug for 1-7 days will be asked to restart at the previous dose. Those not having taken study drug for 8-14 days will restart at half of the prior dose. Those not having taken study drug for 15 days or more will restart the titration. Those who discontinued due to an adverse event will restart at a dose lower than the maximally tolerated dose and titrate to that dose.

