8. MANAGEMENT OF ADVERSE EVENTS

Extensive data regarding safety and adverse events are available from clinical trials of topiramate for epilepsy and episodic migraine. The dose of topiramate to be used in the TopCSPN Study is similar to that used for episodic migraine (50-200mg daily). Adverse events observed in randomized trials for migraine will be summarized⁶⁵. Following this summary, potentially significant adverse events observed at higher doses will be listed.

When topiramate must be discontinued for participant safety, the dose can be stopped immediately or titrated down based on the clinical judgement of the site investigator.

Adverse Events Observed at 100 mg daily of topiramate:

- Anorexia. Loss of appetite is one of the mechanisms contributing to weight loss. Most commonly anorexia is mild. In subjects complaining of intolerable anorexia, the dose will be tapered to the maximal tolerated dose.
- Fatigue. Subjects complaining of intolerable fatigue will be asked to taper the dose to the maximum tolerated.
- Memory Problems. Topiramate may cause confusion, psychomotor slowing, poor concentration, or memory loss. These symptoms are more commonly observed with rapid dose escalation. Patients complaining of intolerable memory problems, or those observed to have cognitive dysfunction sufficiently significant to warrant dose modification in the opinion of the PI will taper their dose to that maximally tolerated.
- Nausea. Subjects complaining of intolerable nausea will be asked to taper the dose to the maximum tolerated.
- Paresthesias. Paresthesias are typically mild and uncommonly lead to discontinuation. In the setting of this study, paresthesias may also be related to the underlying disease (CSPN), or nerve regeneration. There are no data suggesting topiramate causes or worsens peripheral neuropathy. Subjects experiencing increased paresthesias will be encouraged to continue to participate unless the symptom is severe enough in the opinion of the PI to warrant dose reduction.

Potentially serious adverse events noted in the package insert include:

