- Glaucoma. Topiramate has been reported to cause acute myopia associated with secondary angle closure glaucoma. Symptoms typically occur within 1 month of initiating therapy, and include decreased visual acuity and ocular pain. Ophthalmologic findings can include myopia and ocular hyperemia (redness). Mydriasis may or may not be present. Visual acuity will be assessed at each visit and subjects with reduced acuity, ocular pain, or ocular hyperemia will discontinue medication and be immediately referred for ophthalmologic examination.
- Kidney stones. 1.5% of adults exposed to topiramate during its adjunctive epilepsy therapy development reported the occurrence of kidney stones, an incidence about 2 to 4 times greater than expected in a similar, untreated population. Carbonic anhydrase inhibitors (Topiramate, but also zonisamide, acetazolamide or dichlorphenamide) can promote stone formation by reducing urinary citrate excretion and by increasing urinary pH.
- Metabolic acidosis. Hyperchloremic, non-anion gap, metabolic acidosis (i.e., decreased serum bicarbonate below the normal reference range in the absence of chronic respiratory alkalosis) is caused by renal bicarbonate loss due to the inhibitory effect of topiramate on carbonic anhydrase. Renal disease, severe respiratory disorders, status epilepticus, diarrhea, and ketogenic diet may increase this risk. Symptoms may include hyperventilation, fatigue, anorexia, or rarely cardiac arrhythmias or stupor. Serum electrolytes including bicarbonate will be measured at each study visit. Subjects with a total bicarbonate of < 17 mEq/L and a > 5 mEq/L decrease from pretreatment will discontinue treatment.
- Oligohidrosis (decreased sweating) and subsequent loss of temperature regulation with hyperthermia has been reported in adults, especially in combination with carbonic anhydrase inhibitors and anticholinergic medications. Subjects complaining of significant reduction in sweating will taper medication to the maximum tolerated dose.
- Visual field defects (independent of elevated intraocular pressure) have been reported in clinical trials and in postmarketing experience. Visual fields will be assessed at each study

visit. Patients observed to have new visual field abnormalities will be referred for ophthalmologic examination and medication will be discontinued.

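### As worded, the restart rule in 6.13.2 also covers the three safety stops that Section 8 orders, with no exemption and no restart condition

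*Combined protocol and SAP*

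**What the plan says.** Two short sections govern resuming study drug. Section 6.13.1 says of anyone who stops early: "Subjects will be encouraged to restart study drug following the guidelines in section 6.12.2". There is no section 6.12.2; the guidelines are in 6.13.2. That section sets the restart dose by length of interruption and then adds a sentence for one class of stop: "Those who discontinued due to an adverse event will restart at a dose lower than the maximally tolerated dose and titrate to that dose".

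Section 8 orders drug stopped in three situations:

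- Glaucoma: "subjects with reduced acuity, ocular pain, or ocular hyperemia will discontinue medication and be immediately referred for ophthalmologic examination".
- Metabolic acidosis: "Subjects with a total bicarbonate of < 17 mEq/L and a > 5 mEq/L decrease from pretreatment will discontinue treatment".
- Visual field defects: "Patients observed to have new visual field abnormalities will be referred for ophthalmologic examination and medication will be discontinued".

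Section 8 treats most other listed events differently. For nausea, for example, "Subjects complaining of intolerable nausea will be asked to taper the dose to the maximum tolerated". Its general remark on safety stops concerns only the manner of stopping: "When topiramate must be discontinued for participant safety, the dose can be stopped immediately or titrated down", on the site investigator's judgement.

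**The concern.** The adverse-event sentence in 6.13.2 has no limit by type of event, severity or resolution, and its verb is mandatory. A site that follows it literally would put a participant back on blinded drug after an ordered stop for eye symptoms, low bicarbonate or a field defect. Nothing would require the eye examination to have excluded the drug, or the bicarbonate to have recovered. Section 8 presents all three events as effects of topiramate, so the risk of re-exposure falls mainly on the active arm.

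The wording also leaves a cautious site poorly supported. Section 7.1.2 generally classes anything not done as the protocol outlines as a deviation, so a site that sensibly withholds drug has no clear backing in 6.13.2 for doing so.

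**Working it through.** The plan gives no figure to reproduce here. The check is a comparison of texts.

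**Step 1. Which stops does Section 8 order?** Three: the ocular symptoms, the bicarbonate threshold and the new visual field abnormality. Anorexia, fatigue, memory problems, nausea, paresthesias and oligohidrosis are handled by taper or dose reduction. Kidney stones have no stated action. The pregnancy stop is in 6.15 and is not counted.

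**Step 2. Do the three stops fall inside the restart sentence?** Section 6.13, the parent section, lists adverse-event reasons for stopping study medication. They include a clinically significant laboratory change and a residual category of other adverse events. The acidosis stop fits the former and the two eye-related stops fit the latter. Section 6.13.2 uses the same adverse-event category without narrowing it, so all three are inside.

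**Step 3. Does any other text take them out?**

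| Section | What it provides | Limits the restart rule? |
|---|---|---|
| 5.3.2 | Termination visit for those who cannot carry on with drug after an adverse event | No. It does not name the Section 8 stops or mention restarting |
| 6.13 | Investigator may withdraw drug; medical monitor told within 24 hours of adverse-event withdrawals | No. The first is permissive; the second is notice, not approval |
| 6.13.4 | Discussion with site staff when a participant chooses to go off drug | No. It covers the participant's own decision and aims at retention |
| 6.14 | Adverse events followed until resolved or stable, within a time limit | No. The site learns the outcome, but the outcome is not tied to restart |
| 7.1.12 | Investigator reviews laboratory results and judges clinical significance | No |
| 4.2, exclusion 23 | Names metabolic acidosis and closed angle glaucoma as possible risks | No. It is an entry criterion |
| 10.2 and 11.4.1.1 | Use the term permanent discontinuation to define the adverse event collection window | No. Neither says which stops are permanent |

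**Step 4. When is the next required test?** Section 8 says "Serum electrolytes including bicarbonate will be measured at each study visit", and visual fields are also checked at each visit. Visits are 16 weeks apart: 16 × 7 = 112 days. With a window of ±7 days at each end, the gap is 112 − 14 = 98 to 112 + 14 = 126 days. An earlier basic metabolic panel is possible at an unscheduled safety visit under 6.11, at the site PI's choice. The monthly calls can pick up symptoms such as eye pain, but they cannot measure bicarbonate.

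**Result.** Three ordered stops are covered by the restart wording. None is exempted, and none has a restart condition.

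**The case against.** The strongest reply is that 6.13.2 is a dosing schedule. Each of its sentences answers at what dose to resume, for a participant who is fit to resume; none answers whether resuming is safe. The term maximally tolerated dose supports this, because Section 8 uses that idea for taper events and it has no natural meaning after suspected angle closure. A fully literal reading also proves too much: death is among the adverse-event reasons for stopping in 6.13, and nobody thinks the restart rule reaches it. The protocol elsewhere plainly contemplates stops without restart, through the termination visit, investigator withdrawal and continued follow-up off drug.

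Much of this stands. A reader might infer that Section 8 and 6.13.2 directly contradict each other, or that the authors meant these participants to be re-exposed. The documents support neither. Section 8 says when to stop and is silent on restarting, so both instructions can be followed in sequence. The fault is an over-broad rule, and its likely intent was narrow. Nor is the gap between visits a period without observation, since Section 8 orders ophthalmologic referral for both eye-related stops and 6.14 requires follow-up of the event.

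What does not stand is the step from intent to effect. The sentence says that participants with adverse-event stops will restart, and 6.13.1 encourages it. The other provisions allow a site to withhold drug; none says that it should after these three events, or when resuming is acceptable.

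**Conclusion.** The point holds as a modest participant-safety wording fault that should be fixed. The restart text, read as written, reaches three stops that it was probably not meant to reach, and no other section limits it. The conclusion rests on the wording alone. The documents give no expected number of such stops, so no count of participants at risk can be offered, and actual harm would require a site to apply the sentence without clinical judgement.

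A reader might also infer damage to the trial's statistical conclusions. The documents do not support that. Participants are analysed as randomized whether or not they resume drug, and the wording changes neither the models for the co-primary endpoints nor the go/no-go thresholds.

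**What to change.** 1. Limit the adverse-event sentence in 6.13.2, and the encouragement in 6.13.1, to tolerability events that Section 8 handles by taper or dose reduction.
2. State that drug stopped under Section 8 for ocular symptoms or a new visual field abnormality is not restarted unless ophthalmologic examination shows a cause other than study drug. Resolution alone is too loose a condition, because improvement off drug is what a drug effect would produce; the relatedness definitions in 11.4.2 treat it as evidence for causation.
3. State that drug stopped for low bicarbonate is not restarted until a repeat value has recovered to a level set by the sponsor and the investigator judges restart safe.
4. Correct the cross-reference in 6.13.1 from 6.12.2 to 6.13.2.

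The cost is a wording amendment and a note to sites. The ophthalmology referral is already required. An acidosis stop may need one repeat basic metabolic panel, which the unscheduled safety visit in 6.11 already allows. The downside is that a few participants may stay off drug longer, which would slightly dilute the intent-to-treat contrast.

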6.13.3. Missed Doses

Subjects who miss a dose will continue the planned dosing schedule and will not supplement the next dose with that which was missed.

6.13.4. On Study/Off-Intervention Evaluations

Every possible effort should be made by the site PI to encourage subjects who are no longer taking study drug to remain in the study. They should explain that continued participation will teach us more about the natural history of CSPN progression, the impact of metabolic improvement and weight loss on CSPN, and the clinical relevance of IENFD and other surrogate measures of CSPN progression.

When subjects decide to go off the study drug, it will be a reportable event and the project manager will discuss the reasons for this with site staff to learn the specifics in each case and provide advice on an individual basis about the best ways to keep the subject engaged in the

project. These subjects and their physicians will not be told whether they were given topiramate or placebo.

6.14. Off-Study Requirements

Adverse events will be followed up to 30 days after study completion (including early termination) or until the site Principal Investigator deems the condition to have resolved or the condition has stabilized (whichever occurs first).

6.15. Pregnancy

Women who become pregnant while in the study will have the study drug withdrawn immediately, will be asked to return for a final in-person evaluation, and will be followed according to adverse event reporting procedures until birth or conclusion. Generally, follow-up will not exceed 8 weeks following the estimated delivery date.

6.16. Diabetes

Patients who meet ADA criteria for diabetes at screening will be excluded. Those who develop diabetes during the course of the study may continue in the study. However, in the event a participant is found to have diabetes on follow up metabolic testing, their primary care provider will be notified.

7. SPECIAL INSTRUCTIONS AND DEFINITIONS OF EVALUATIONS

7.1.1. Informed Consent

Written informed consent will be obtained from each participant before any study-specific procedures or assessments are performed and after the aims, methods, anticipated benefits, and potential hazards are explained. The participant's willingness to participate in the study will be documented in writing in a consent form, approved by the NeuroNEXT CIRB, which will be signed by the participant with the date of that signature indicated. The investigator will keep the original consent forms and copies will be given to the participants. It will also be explained to the participants that they are free to refuse entry into the study and free to withdraw from the study at any time without prejudice to future treatment. Written and/or oral information about the study in a language understandable by the participant will be given to all participants. HIPAA guidelines for confidentiality and the principles of medical ethics will be adhered to during the study.

7.1.2. Protocol Violations

The site monitor is responsible for collection of all protocol deviations that occur during the course of the study to ensure proper reporting in the clinical study report.

Generally, any activity that is not performed as outlined in the protocol should be categorized as a 'Protocol Deviation'. Missed visits and any procedures not performed (not attempted) for reasons other than illness, injury or progressive disability (i.e., subject is physically unable to

perform test) will be reported as protocol deviations. Procedures or visits not performed due to illness, injury or disability, including procedures that were attempted but failed (i.e., blood samples unable to be drawn after multiple attempts, or weight unable to be obtained due to subject immobility) will not be reported as protocol deviations. Deviations fall into two categories, 'major' and 'minor', and are defined as follows:

Major: Any deviation that impacts safety, welfare, or rights of a study subject, or impacts the primary outcome of the study (safety assessments). Examples include: Informed Consent issues affecting a subject's rights, Inclusion/Exclusion violations, Missed Assessments affecting safety endpoints, Study Drug Administration that affects a study endpoint or the subject's welfare. A major deviation is also termed a protocol violation.

Minor: Any deviation that does not fall within the above category. Examples include: out of window or missed study assessments that do not affect study endpoints or the subject's welfare.

7.1.3. Medical History

A complete medical history including lifestyle questions (i.e., tobacco and alcohol use) will be obtained at screening and prior to randomization.

7.1.4. Concomitant Medications/Treatments

All concomitant medications must be recorded, including, but not limited to all vitamins, supplements, nutritional, herbal and alternative therapies.

7.1.5. Physical Examination

A general medical and detailed neuromuscular physical examination will be performed in order to exclude medical conditions precluding participation, and to confirm symptoms consistent with distal symmetric polyneuropathy. The neurological examination will include a baseline assessment of visual fields.

7.1.6. Vital Signs

Vital signs will be obtained after the subject has been sitting for five minutes. Vital signs include blood pressure (systolic and diastolic), heart rate (beats/minute), and body temperature (°C).

7.1.7. Waist Circumference

Waist circumference will be measured in centimeters (cm) while standing. Measurement will be performed at the level of the iliac crest after expiration.

7.1.8. Electrocardiogram (ECG)

An electrocardiogram (ECG) will be performed to exclude a baseline prolonged QTc interval. ECGs with QTc interval more than 430 ms in men, or 450 ms in women will be reviewed at each

site. Participants with QTc more than 450 ms in men, or 470 ms in women will be considered screen failures. Electrocardiogram's are not required to be reviewed by the site cardiologist.

7.1.9. Neuropathy Symptom Assessment

*Neuropathy Total Symptom Score -6 (NTSS-6)*⁵³ is a brief inventory of neuropathy symptoms that has demonstrated reliability and validity in diabetic neuropathy.

Brief Pain Inventory – Diabetic Neuropathy (BPI-DN)^{54,55} is a validated pain inventory that assesses pain severity related to CSPN.

7.1.10. Utah Early Neuropathy Scale (UENS)

*Utah Early Neuropathy Scale (UENS)*⁴⁸ will be performed by the investigator to confirm diagnosis and exclude patients with severe neuropathy.

7.1.11. Functional and Mobility Testing

Functional and mobility testing, fitness and proactive balance will be assessed because balance and fall risk are major clinically relevant outcomes for patients with CSPN.

- *A 6-minute walk test (6MWT)* will be performed on a standard course that will be used throughout the study. The 6MWT has demonstrated reproducibility in obese participants⁵⁶ and has been shown to correlate with intermuscular adipose tissue, a depot of adipocytes related to insulin resistance and increased in patients with metabolic syndrome⁵⁷.
- *A Timed up and Go (TUG)* will be performed as a measure of proactive balance and fitness. TUG times are normally distributed, resistant to ceiling effects⁵⁸ and are reduced in patients with neuropathy in the setting of diabetes relative to control participants⁵⁹. Among commonly employed fall risk assessments, the TUG had the highest diagnostic accuracy⁶⁰.
- The Activities-specific Balance Confidence (ABC) Scale. The ABC scale is a self-administered instrument assessing balance and gait confidence.⁸⁹

7.1.12. Laboratory Evaluations

Clinical laboratory evaluations for the study will be analyzed by the NeuroNEXT central laboratory at the University of Rochester. Refer to the *University of Rochester Medical Center Lab Manual* for sample handling and processing requirements.

The following laboratory assessments will be performed throughout the study:

- Safety monitoring laboratory tests:
 - Complete Blood Count (CBC)
 - Basic Metabolic Panel (BMP) including Sodium, Potassium, Chloride, Carbon Dioxide, Urea Nitrogen, Glucose, Creatinine, Calcium, and Anion Gap (optional).
 - Hematology Panel
 - Serum Pregnancy Test (for women of child-bearing potential only)
 - Urine Pregnancy Test (for women of child-bearing potential only)

NN108 Topiramate as a Disease Modifying Therapy for CSPN

Version 8.0

Version date 8/8/2018

- Baseline metabolic monitoring laboratory tests. These are intended to assess the metabolic effects of therapy and to confirm the presence of metabolic syndrome for inclusion criteria and evaluation throughout the study:
 - Fasting Insulin
 - Fasting Lipid Panel including Cholesterol, Triglycerides, Calculated LDL Cholesterol, and HDL Cholesterol.
 - 2-hour Oral Glucose Tolerance Test (OGTT) using a 75g anhydrous dextrose oral load with the first blood draw (pre-dextrose) prior to 10 am. The second draw will be 2 hours post dextrose. The subject will remain sedentary during the following two hours.
 - HgbA1C
- Laboratory evaluation for additional causes for neuropathy:
 - Vitamin B12
 - Serum Immunofixation
- Serum topiramate levels will be measured at Baseline and weeks 32, 64, and 96 (or ET) in order to assess for compliance and treatment crossover.

Participants will be asked to hold their morning dose of study medication until after the blood draw at weeks 32, 64, 96/ET. The date and time of last dose of study drug will be recorded. If the participant does not hold the prior dose, the topiramate level should still be obtained.

Topiramate laboratory kits, shipping materials, and requisitions will be provided by Utah. The sample will be obtained in a red collection tube with serum separated by centrifuge within 2 hours. Serum will be placed in the transport vial and refrigerated prior to being placed on a cold pack for shipment. The sample will be returned to Utah with the skin biopsy sample. Samples should be received by Utah cool (not frozen). The results will be made available to the DSMB.

- DNA sample (OPTIONAL)
DNA samples can be collected at Baseline using supplies provided by URM. Centrifuge the EDTA tube at 1500 RPM for 15 minutes. The buffy coat will be transferred into cryovials and stored at -80C. At the end of the enrollment period, sites will batch ship all the buffy coat samples to Utah with shipment kit and air bills provided.

All clinical and laboratory evaluations, procedures related to inclusion/exclusion criteria, or assessments performed during treatment will be reviewed, initialed and dated by the Principal Investigator or the individual(s) specifically designated by the investigator on the DOR log. The Investigator must indicate if out of range lab values are Clinically Significant (CS) or Not Clinically Significant (NCS) on the lab report.

